3.3 Secondary aims

- 1) To monitor and report the aggregate **signs** of AF related arrhythmias as measured by an implanted ILR during months 0 to 6 at follow-up after WACA-PVI + LAPWI.
To monitor and report the **symptoms** of arrhythmia with validated questionnaires during the first 6 months F-U post procedure. QOL studies.
- 2) Repeat the above for 6 - 12 months post procedure.

PeAF box feasibility ver 2.3

3.4 Hypothesis (see paragraph 3.2, safety)

H₁: By esophagoscopy the day after successful WACA-PVI + LAPWI the proportion of inflammation or visible injury in the esophagus induced by the ablation procedure is less than 0.3

H₀: By esophagoscopy the day after successful WACA-PVI + LAPWI the proportion of inflammation or visible injury in the esophagus induced by the ablation procedure is more than or equal to 0.3

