3.2 Primary aims

In patients who undergo first ablation for PeAF with WACA-PVI the addition of anchored lines connecting the zeniths of the superior pulmonary veins (roof) and the nadirs of the inferior pulmonary veins with proven isolation of the LA posterior wall (LAPW-isolation, LAPWI) is feasible, safe and durable.

Feasibility: **Descriptive:** In patients with PeAF and established WACA-PVI it is possible to establish complete electrical isolation (bidirectional conduction block) of the LAPW by ablating a superior and inferior line connecting the PVs within a reasonable prolongation / increase of procedure-, ablation- and fluoroscopy time.

Safety: **Hypothesis to be tested (see 3.4).** Guided by a temperature probe in the esophagus WACA-PVI+LAPWI can be achieved without increasing the incidence of inflammation/ injury to the esophageal epithelial lining as proven by endoscopy on the day after the procedure and compared to reported incidences of up to 30% in recently published studies.

Descriptive: WACA-PVI+LAPWI can be achieved without increasing the risk of pericardial effusion and tamponade as proven by post-procedure TTE.

Durability: **Descriptive:** At a *per protocol* interventional control procedure (independent of symptoms) 3 months after the index procedure a large proportion of LAPWs of PV's will remain durably isolated.

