Esophagus data (hypothesis testing, safety): Endoscopies will be performed the day after the procedure and video material from each endoscopy will be evaluated by two independent gastroenterologists. If any reaction or other pathology is encountered in the esophagus any decision on follow-up or treatment will be at the discretion of the gastroenterologist.

All data and calculations obtained in this study will be kept on storage for 5 years after the results have been published.

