3.7 Statistical Considerations

There will be no randomization or direct between-groups comparisons. Although this study is primarily exploratory and descriptive in nature we will formally test the hypothesis given in paragraph 3.4. Thus the sample size calculation of this study hinges on the need to demonstrate - with a reasonable power - that putative esophageal reactions to the WACA-PVI + LAPWI procedure do not exceed earlier findings after PVI alone.

PeAF box feasibility ver 2.3Calculation of sample size and power:

a) The outcome of esophagoscopy on day 1 after ablation in the LA is considered to be either positive (inflammation or other esophageal reaction is noted) or negative (no reaction). Therefore the probability distribution of outcomes of esophagoscopy will behave binomially.

b) Recent data indicate that esophageal reactions can be observed in the range of 10 % (proportion = 0.1) up to 30 % (proportion = 0.3) with the second generation ablation technology. We would be interested in showing that the proportion of esophageal reactions to WACA-PVI + LAPWI does not exceed proportions reported earlier (i.e. render probable that the proportion of any visible esophageal reaction to ablation is less than 0.3)

c) Setting as comparator that the underlying proportion (P) of patients subjected to this treatment that experience esophageal reactions is 0.3 or more AND assuming that the "true" proportion in our study is 0.1 then when:

- P =	0.3
- One-tailed α =	0.05
- "true" proportion =	0.1

- recruiting 23 patients will yield 80 % power to reject the (H_0) hypothesis that the proportion experiencing esophageal reactions is equal to or higher than the 0.3.

Based on these calculations we aim to recruit 23 patients for the study.

The above computations were aided by the software program (IBM/ SPSS - Sample power ® ver. 3.0.1)

Post - hoc analyses: Statistical analysis of input - and output data will be performed using IBM/SPSS ® ver. 22 using appropriate statistical methods.

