3.8 Risks, inconvenience and patient exposure to adverse events

A) Since participating patients are all scheduled for PVI the added risk relate to the elements added by the study protocol. Directly related to the procedure are: 1) Added ablation (LAPW) compared to PVI alone. This increases the amount of ablation with estimated 30%, increases the total procedure time with an estimated 10% and increases the total fluoroscopy dose area product (DAP) with an estimated 5-10%. 2) A mandatory second procedure after 3 months. This procedure will be minor in most patients.

B) Risk to the oesophagus. Although inflammatory reactions and even devastating fistulae after ablation at or near LAPW are mentioned in the literature (including recently). We have never in our setting (15 years) experienced any clinical manifestations of damage to the oesophagus when performing ablation procedures - including PVI + BOX lesion sets. On the other hand this has not been studied systematically with oesophagoscopy. Thus the detection of subclinical superficial in-

PeAF box feasibility ver 2.3

flammation of the oesophageal wall in this study is a possibility and is in fact *the pivotal safety parameter under study*. The oesophagus temperature is monitored closely with a temperature probe during the procedures and the ablation process is tailored to avoid damage.

C) X-ray exposure. It is estimated that adding BOX to PVI in the first procedure will add extra 0,5 mSv. and the obligatory follow up procedure after 3 months an extra 3-4 mSv. This might increase the lifetime risk of developing mortal cancer from around 45% to 45,01 % (one in 10000 pts.).

D) Implantation of loop recorder (ILR). Is a minor surgical maneuver with subcutaneous insertion of a chip measuring 2 mm * 3 mm * 40 mm performed while the patient is still under full anesthesia at the end of the ablation procedure. The overall rate of adverse events related to that device is an estimated 1% - 2% including pain and local infection.

E) Oesophagoscopy the day after the procedure. This is a common invasive routine procedure performed by a highly skilled gastroenterologist. International literature estimates the overall complication rate to around 0,1%. However up to 2 % of patients may experience soreness of throat or annoying belching post procedure. The procedure is done under light sedation and overall this added oesophagoscopy is estimated to delay discharge for two hours.

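### The only formal safety test is worded for patients with successful isolation, its power calculation for all treated patients, and no rule says how failed isolations count

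*Combined protocol and SAP*

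**What the plan says.** Section 3.4 states one pair of hypotheses. H1 and H0 both begin "By esophagoscopy the day after successful WACA-PVI + LAPWI the proportion of inflammation or visible injury in the esophagus"; H1 puts that proportion below 0.3 and H0 at 0.3 or above.

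Section 3.7 says "we will formally test the hypothesis given in paragraph 3.4", then sets out the test in terms that carry no success condition:

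- Item a: "The outcome of esophagoscopy on day 1 after ablation in the LA is considered to be either positive" or negative.
- Item c: the comparator is that "the underlying proportion (P) of patients subjected to this treatment that experience esophageal reactions is 0.3 or more".
- Sample size: "recruiting 23 patients will yield 80 % power to reject the" null hypothesis. The 23 are patients recruited, with no allowance for failed isolation.

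The endoscopy schedule is also unconditional. Section 3.6.3 says "Endoscopies will be performed the day after the procedure and video material from each endoscopy will be evaluated by two independent gastroenterologists", and the Appendix A flow sheet places it on day 1 for everyone.

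Failed isolation is foreseen in two places. Section 3.6.3 declares posterior-wall isolation (LAPWI) not achievable if it is not reached within 20 minutes of additional ablation time. Appendix B, part B, item 6 labels LAPWI or PVI not feasible when block cannot be obtained under the esophageal-temperature algorithm. Neither place says whether such patients are counted, left out or replaced in the esophageal test.

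**The concern.** Section 3.8 calls esophageal injury "the pivotal safety parameter under study", and it is the only outcome tested formally; the other aims are descriptive. The two sections give this test different denominators.

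The difference is not neutral. A patient whose isolation fails has still had left-atrial ablation. One route to failure comes after extra ablation up to the time limit, and the other comes through an algorithm driven by esophageal heating. Success is thus a post-treatment event that may be related to the outcome. The sign of any bias cannot be fixed from the documents: failed patients could have more lesions because the esophagus was heated, or fewer because the algorithm limited energy at hot points.

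Two things are at stake. The decision on H0 can depend on which reading is chosen, and that choice could be made after the data are seen. The study is also meant to inform a randomized trial, which would need the injury rate in all patients in whom the strategy is attempted.

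**Working it through.** **Inputs.** From Section 3.7: null proportion 0.3, assumed true proportion 0.1, one-sided α = 0.05, N = 23, power 80%. The documents give no failure rate and no injury rate among failures, so both are assumptions below. Section 3.7 names no test, so three are shown.

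**The plan's own figure.** With the arcsine approximation, h = 2·asin√0.3 − 2·asin√0.1 = 0.5158. Power at N = 23 is Φ(0.5158·√23 − 1.645) = Φ(0.829) = 79.6%, which matches the stated 80%. That holds only if all 23 enter the test. With one, three or five patients left out, the same formula gives 78.1%, 74.6% and 70.7%.

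**One-sided p-values against 0.3**, for x lesions in n patients:

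- Exact: P(X ≤ x), X ~ Bin(n, 0.3).
- Score: Φ(z), z = (x/n − 0.3)/√(0.21/n).
- Arcsine: Φ(z), z = 2[asin√(x/n) − asin√0.3]·√n.

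Largest lesion count that rejects H0:

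| n | 23 | 22 | 21 | 20 | 19 | 18 |
|---|---|---|---|---|---|---|
| Exact | 2 | 2 | 2 | 2 | 2 | 1 |
| Score | 3 | 3 | 2 | 2 | 2 | 2 |
| Arcsine | 3 | 3 | 3 | 2 | 2 | 2 |

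**One failed patient who has a lesion** (H0 kept on all treated, rejected on successes only):

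| Test | All treated | Successes only |
|---|---|---|
| Exact | 3/23, p = 0.054 | 2/22, p = 0.021 |
| Score | 4/23, p = 0.093 | 3/22, p = 0.047 |
| Arcsine | 4/23, p = 0.076 | 3/22, p = 0.029 |

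**Several failed patients, none with a lesion** (H0 rejected on all treated, kept on successes only):

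| Test | Failures | All treated | Successes only |
|---|---|---|---|
| Score | 2 | 3/23, p = 0.038 | 3/21, p = 0.058 |
| Arcsine | 3 | 3/23, p = 0.022 | 3/20, p = 0.052 |
| Exact | 5 | 2/23, p = 0.016 | 2/18, p = 0.060 |

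**Probability that the two readings disagree.** With f failures, let k ~ Bin(f, q) be lesions in failures and s ~ Bin(23 − f, p) lesions in successes. Sum the joint probabilities where the decision on (s + k)/23 differs from that on s/(23 − f):

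| Assumed rates | f | Exact | Score | Arcsine |
|---|---|---|---|---|
| p = q = 0.1 | 1 | 2.8% | 2.1% | 2.1% |
| p = q = 0.1 | 2 | 5.7% | 16.5% | 4.1% |
| p = q = 0.1 | 3 | 8.5% | 14.7% | 14.7% |
| p = 0.1, q = 0.3 | 1 | 8.4% | 6.2% | 6.2% |
| p = 0.1, q = 0.3 | 2 | 16.8% | 12.3% | 12.7% |
| p = 0.1, q = 0.3 | 3 | 24.9% | 13.4% | 13.4% |

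These totals pool both directions. For the score test with two failures, 16.2 of the 16.5 points at equal rates, and 9.8 of the 12.3 points at q = 0.3, are cases where testing successes only is the stricter reading. For all three exact-test rows in each block, every disagreement is in the lenient direction.

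**The case against.** The strongest reply is that Section 3.7, the only statistical section, already points to all treated patients in its outcome, proportion and sample size; that endoscopy is scheduled for everyone; and that the not-achievable and not-feasible labels serve the feasibility description. On this view the word in 3.4 is loose drafting. Much of this stands: all treated patients is the better-supported reading. It does not close the question. Section 3.7 refers back to 3.4 for the hypothesis, and Section 3.2 frames the safety aim as showing that "WACA-PVI+LAPWI can be achieved without increasing the incidence of inflammation/ injury to the esophageal epithelial lining", which also fits a success-only reading. If 3.7 is what was meant, both hypotheses are misworded.

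Second, the effect depends on assumed failures. Section 2.3 reports that proven LAPWI is relatively fast in most patients, and Appendix B allows repeat and adjacent attempts before failure is declared. With no failures the readings coincide; with one failure and equal injury rates they disagree only 2.1–2.8% of the time. That stands as a limit on the size of the point.

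Third, the larger equal-rate figures do not measure selection bias. They arise mostly because a smaller n crosses a discrete rejection limit, and there success-only testing makes a safety claim harder. That is correct. The q = 0.3 rows are closer to the selection concern, although some of their score and arcsine totals also contain stricter cases.

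Fourth, a set defined by LAPWI having been started is itself a mild post-treatment condition, since it comes after PVI. That is true, and it is why patients with left-atrial ablation but no LAPWI attempt should be described separately.

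**Conclusion.** The concern holds. The hypotheses as written restrict the study's only formal safety test to successful isolations, the power calculation does not, and nothing in the plan reconciles them. The textual mismatch is certain; its effect on the result depends on how many isolations fail and on the lesion rate in those patients, neither of which the documents give. One lesion in one failed patient is enough to turn H0 kept into H0 rejected under each of the three tests, and failures without lesions can do the reverse. The direction of bias is unknown. The point should be fixed before analysis; with 23 patients and a one-sided test, a single patient can decide the conclusion.

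**What to change.** - Delete the success condition from H1 and H0 in Section 3.4 so that they agree with Section 3.7.
- In Section 3.7, define the primary safety set as all patients in whom LAPWI ablation was started at the index procedure, whether or not isolation was achieved.
- Describe separately the successful-isolation subset and any patients with left-atrial ablation but no LAPWI attempt.
- Report the number of missing day-1 endoscopies, with a sensitivity analysis counting them as positive.
- Name the test in Section 3.7, because the decisive lesion count at n = 23 is 2 for the exact test and 3 for the score and arcsine tests.

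The cost is wording and minor analysis work. Endoscopy is already scheduled without a success condition, so no procedure, visit or patient is added. The one downside is that the reported rate may be less favourable than the success-only rate, though it could equally be more favourable.

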3.5 Flow sheet

See appendix A

3.6 Methods

A non-randomized single center study with consented participation of 23 eligible consecutive patients referred for radio frequency ablation for PeAF

3.6.1 Inclusion criteria:

- Symptomatic PeAF (EHRA Symptom class II or more).
- Failing at least one AAD class I-IV.
- Aggregate duration of persistent AF more than 3 months and less than 12 months. during any time period prior to study entry.
- Age between 18 years and 80 years.

3.6.2 Exclusion criteria:

- Former ablation or surgery in the left atrium.
- Former valve surgery.
- LA diameter (TTE-PLAX) > 52 mm in males and > 47 mm in females
- Severe mitral valve disease (stenosis or regurgitation) .
- LVEF < 35 %.
- Implanted pacemaker or ICD leads.
- Pregnancy or susceptibility to that.
- Severe other disease that may hamper adherence to study protocol.
- Intolerance to amiodarone.
- Participation in other clinical research studies.

3.6.3 Data handling

The procedures will be conducted in compliance with our standards for AF ablations and as specified in appendices A and B. All data to be analyzed in this study will be generated within the framework of this study protocol. There will be no transfer of data from the patient's hospital files to the study other than data generated as part of this study

PeAF box feasibility ver 2.3Descriptive data:

Feasibility: Time consumption (min.), use of X-ray (mGy), ablation time (min.) and energy delivery (watt x sec.) are registered when WACA-PVI is completed and compared to the same values at the end of the procedure. An estimate of the percentage increase of the procedure parameters due to the added LAPWI will be calculated. In the event that LAPWI cannot be achieved within *20 min additional ablation time* after WACA-PVI then LAPWI will be considered *not achievable*.

Safety: The unlikely occurrence of pericardial effusion will be estimated and measured by TTE from subxiphoid and parasternal windows immediately after the procedure and compared to preprocedure echo measurements.

Durability: At the follow-up procedure after 3 months a single transseptal puncture will be done and the durability of bidirectional block of the PV's and the LAPW will be checked with a soft 20 polar catheter (Pentarray®). If electrical conduction gaps in the ablation lines are detected a second TS puncture will be performed and an ablation catheter inserted into the LA. Then the precise localization of gaps will be noted and related to the data from the index procedure (force-time integral, ablation index, esophagus temperature) for each point before gap closure with RFA. **Secondary aims (paragraph 3.3):** The patients will be asked to answer the AFEQT 20 item validated questionnaire³⁴ (see ref.; full questionnaire not append in protocol) on quality of life in patients with atrial fibrillation prior to the ablation and at 3, 6 and 12 months post ablation. The implanted ILR will be programmed to diagnose AF and AF related arrhythmias with the best achievable sensitivity and specificity. There will be a routine reading and clearing of device at 1, 3, 6, 9 and 12 months after the index procedure. Further the patients will be instructed to have the device read if they experience palpitations or other AF related symptoms.

Esophagus data (hypothesis testing, safety): Endoscopies will be performed the day after the procedure and video material from each endoscopy will be evaluated by two independent gastroenterologists. If any reaction or other pathology is encountered in the esophagus any decision on follow-up or treatment will be at the discretion of the gastroenterologist.

All data and calculations obtained in this study will be kept on storage for 5 years after the results have been published.

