- Third generation technological developments to optimize ablation lesions using contact force (CF) and *time-force-temperature-impedance* integration have become an integral part of AF- related procedures in our EP lab. Moreover, recently the *surround flow technology* (SF) offering even more efficient cooling than seen before has been integrated with the Smarttouch ® technology.
- Rigorously proving bidirectional electric block over all ablation lines to ensure PVI and LAPW isolation.
- Allowing proper intra-procedural waiting time supplied with adenosine testing for dormant conduction to detect and ablate early re-conduction.

Caveats - collateral damage

With larger lesion sets (such as PVI + LAPWI) and more efficient lesions - e.g. with SF Technology - the risk of damaging tissue surrounding the LA might increase. Most importantly the esophagus is notoriously prone to heat related lesions, ulcerations and eventually fatal fistulae. 2010 Halm et al. from Leipzig ³¹ published their data on 185 patients monitored with an esophageal temperature probe during LA ablation procedures. At esophagoscopy 1 day post procedure they found RFA related lesions in 14,5 % of the patients ranging from small superficial ulcer-like lesions to larger hemorrhagic lesions. Maximal esophageal temperature averaged 41,4 ° C in patients without lesions and 42,6 ° C in patients with lesions. No lesions were found if max temperature was ≤ 41 ° C. Later Knopp et al ³² found superficial thermal esophageal lesions in 11 % of 425 patients undergoing LA ablation using a cooled tip catheter in a steerable sheath. However, recently a Japanese group, per-

PeAF box feasibility ver 2.3

forming PVI for AF, allowed esophagus temperatures up to 42 ° C before pausing ablation. They found a range of lesions from erythema to frank ulcers in 25% of patients ³³.

Burning questions in ablation for PeAF - Aims of study:

There needs to be done a sufficiently powered randomized multicenter trial utilizing the latest technology to clarify if LAPWI as an adjunct to PVI is beneficial as a first procedure strategy in PeAF.

However, because of the substantial economical and logistical burden of such a study we suggest to first conduct a minor non-randomized, single center study. The aims of such as study is to clarify:

- 1) Utilizing SF-Smarttouch technology is it feasible to obtain PVI + LAPWI within a reasonable procedure- and fluoroscopy time ?

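### No safety outcome is defined after day 1 or after the day-90 procedure, and the hospital-file rule leaves late events treated in routine care without a clear route into the results

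*Combined protocol and SAP*

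**What the plan says.** The aims listed at the end of section 2.3 ask whether the procedure is safe, and section 3.2 makes safety one of three primary aims. Two measurements carry that aim. The tested one is oesophagoscopy on day 1; section 3.4 sets the null as "the proportion of inflammation or visible injury in the esophagus induced by the ablation procedure is more than or equal to 0.3". The descriptive one is a TTE for pericardial effusion, done "immediately after the procedure and compared to preprocedure echo measurements" (section 3.6.3).

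The protocol also names harms beyond these two. Section 2.3 warns that "the esophagus is notoriously prone to heat related lesions, ulcerations and eventually fatal fistulae". Section 3.8 lists fistula again, loop-recorder (ILR) adverse events at 1% to 2%, endoscopy complications, amiodarone effects and "A mandatory second procedure after 3 months". If the day-1 endoscopy shows pathology, "any decision on follow-up or treatment will be at the discretion of the gastroenterologist"; nothing says that the outcome is to be recorded.

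Later contacts exist. Section 3.6.3 gives device readings at 1, 3, 6, 9 and 12 months and the AFEQT questionnaire at 3, 6 and 12 months. Appendix A gives the day-90 re-procedure. Their stated content is arrhythmia, quality of life and durability of the lines.

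On data sources, section 3.6.3 limits the analysis to data generated under the protocol and states: "There will be no transfer of data from the patient's hospital files". The same sentence goes on to exempt data that the study itself generates.

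**The concern.** The safety question is open-ended, but the defined observation for it stops the day after the first procedure. Three gaps follow.

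- A complication that shows itself after day 1 has no endpoint, definition, collection window or form.
- The day-90 procedure involves a transseptal puncture in every patient and, where gaps are found, a second puncture and further ablation. No safety assessment is listed after it.
- The usual way to recover unplanned events, the hospital record, is restricted by the data rule.

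A patient with a clean day-1 endoscopy and a later serious complication would be a negative in the only formal test and need not appear anywhere else. Section 2.3 says that the results are to inform a randomised trial, and section 3.14 foresees a publication stating that the procedure can be done safely. A reader of that publication would take the statement to cover more than one day.

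**Working it through.** **1. The plan's own figure.** Section 3.7 gives N = 23 and 80% power for a true proportion of 0.1 against 0.3, with "One-tailed α" of 0.05. The one-sided arcsine formula reproduces it:

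- h = 2·arcsin(√0.3) − 2·arcsin(√0.1) = 0.516
- n = ((1.645 + 0.842)/0.516)² ≈ 23.2
- power at n = 23: Φ(0.516·√23 − 1.645) ≈ 79.6%

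This figure concerns the day-1 endoscopy alone. Nothing in the present point changes it.

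**2. Harms set against measurements.**

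| Harm | Where named | Defined measurement | Route into the results under 3.6.3 |
|---|---|---|---|
| Oesophageal reaction on day 1 | 3.2, 3.4 | Oesophagoscopy | Defined, tested |
| Effusion or tamponade at the index procedure | 3.2, 3.6.3 | One TTE | Defined, descriptive |
| Fistula | 2.3, 3.8 B | None after day 1 | None defined; may be excluded if treated in routine care |
| Tamponade after the first TTE | Not named separately | None | As for fistula |
| Outcome of a day-1 lesion | 3.6.3 | None; follow-up is discretionary | Unclear |
| ILR-site events | 3.8 D | None | Can be read as study-generated; no form or endpoint |
| Endoscopy complications | 3.8 E | None | As for ILR |
| Amiodarone effects | 3.8 F | Tolerance decides exclusion in the run-in; no reporting stated | As for ILR |
| Complications of the day-90 procedure | 3.8 A | None | As for ILR |

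**3. Coverage.** There are 23 index procedures and 23 day-90 procedures if nobody drops out: 23 + 23 = 46. The defined safety measurements belong to the first 23, that is 23/46 = 50%. In time, they cover about 1 day of the 360-day schedule in Appendix A.

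**4. Size of one event.** 1/23 = 4.3% of patients.

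**5. What collection could and could not show.** With n = 23 and a true rate p, the chance of seeing at least one event is 1 − (1 − p)²³.

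| p | Source | Chance of at least one event |
|---|---|---|
| 0.5% | Assumption | 10.9% |
| 1% | Section 3.8 D (ILR) | 20.6% |
| 2% | Section 3.8 D (ILR) | 37.2% |
| 5% | Assumption | 69.3% |

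With zero events, the exact one-sided 95% upper bound is 1 − 0.05^(1/23) = 12.2%. Without systematic collection, even this bound could not be stated, because an absent report would not be an observed zero.

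**The case against.** A reader might infer from the hospital-file sentence that no late event can enter the results. The documents do not support that.

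- The exception for study-generated data matters. The ILR implant, the endoscopy, the amiodarone course and the day-90 procedure are all part of the protocol, so complications seen there can reasonably be read as inside it. For these the gap is a missing definition and form, not a prohibition.
- Even a fistula treated elsewhere could be reported by the patient at a study contact, and that report would be study data.

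Nor can one say that the later contacts gather nothing but device readings and questionnaires. The budget in section 3.12 allows four one-hour visits per patient, separately from the ILR work, and does not describe their content.

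A reader might also multiply the 10% to 30% range in section 3.7 by 23 and conclude that 2 to 7 lesion outcomes would be lost. That range counts any visible reaction. The documents do not say how many reactions would be followed up, and they do not exclude the outcome from the study.

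It is also fair to say that the test is correct for its hypothesis, which concerns day 1 only; that the study calls itself mainly exploratory; and that 23 patients cannot establish the rate of a rare harm.

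What remains is that capture of late harm would depend on chance and on how one sentence is read. A small sample limits what collected counts can prove, but is no reason to leave serious events uncounted.

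**Conclusion.** The point holds in a limited form. No safety endpoint or adverse-event collection is defined after day 1 of the index procedure, and none after the day-90 procedure, although the study asks a general safety question and names later harms itself. For events at protocol procedures, the route into the results is unspecified. For a late fistula or tamponade treated in routine care, there is no defined route and a plain reading of section 3.6.3 may exclude it. The same is possible for the outcome of discretionary oesophageal follow-up.

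Half of the planned left-atrial procedures lack a defined safety assessment, and each unrecorded event is 4.3% of the sample. The sample size, α and the planned test are unaffected.

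This rests on three assumptions: that a fistula or effusion can present after day 1 (the documents give neither timing nor rate); that all 23 patients reach day 90; and that no collection plan stands in material not available for review, such as the consent pages or the flow-sheet figures. The text of Appendix A lists no such plan.

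**What to change.** 1. Amend section 3.6.3 so that hospital records on complications, and on the outcome of any oesophageal follow-up, may be used. Check that the consent wording matches.
2. Record a fixed adverse-event list at the existing 1, 3, 6, 9 and 12-month contacts and after the day-90 procedure: oesophageal symptoms or fistula, effusion or tamponade after the first TTE, ILR-site events, endoscopy complications, amiodarone adverse effects, and complications of the day-90 procedure.
3. Report counts separately for the index and day-90 procedures, each with an exact confidence interval and the number of patients actually followed. State beside any zero that it still allows a rate up to about 12% (one-sided 95%, n = 23).
4. Label the endoscopy and TTE conclusion as acute safety of the index procedure only.

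The cost is a protocol amendment, a short checklist, and a safety profile that may look less favourable. No extra examination or change in sample size is involved. The plan has five device readings but budgets four visits, so some contacts may be remote or coincide with day 90; the questions could then be asked by telephone. The change should come before or early in data collection, because events not asked about at the time may not be recoverable later.
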